## Study Summary

|                           |   |
|---------------------------|---|
| Title              | Randomized study of cranial blocks for postoperative anesthesia to reduce pain and postoperative opioid usage  |
| Short Title        | Cranial blocks for postoperative anesthesia   |
| IRB Number         | 834603  |
| Protocol Number    | N/A   |
| Methodology        | Prospective single-blinded randomized controlled trial  |
| Study Duration     | 12 months   |
| Study Center(s)    | Single-center   |
| Objectives         | Primary: 

• To assess the effectiveness of analgesia by scalp nerve block with various agents in the first 72 hours following elective craniotomy.

 |
| Number of Subjects | 90  |

|  |   |
|--|---|
| Main Inclusion and Exclusion Criteria | 
Inclusion Criteria
 
 
• <math>\geq 18</math> years of age
 
• Need for elective supratentorial craniotomy
 
• Preoperative GCS <math>> 13</math>
 
 
Exclusion Criteria
 
 
• Preoperative GCS <math>\leq 13</math>
 
• Child (<math>< 18</math> years of age)
 
• Inability to understand or use the visual analog scale (VAS)
 
• Proven or suspected allergy to local anesthetics
 
• Craniotomy incision extending beyond the field of the block
 
• Patients chronically (more than 2 wk) treated with narcotic medications
 
• Previous scalp incision
 
• Bilateral craniotomies
 
• Allergies to local anesthetics
 
• GCS verbal score <math>< 4</math> after extubation
 
• Patients whose surgeries exceed 6 hrs (will be removed from study and maintained with standard of care)
 
• Patients currently on ergot-type oxytotoxic drugs, MAOIs, or certain antidepressants
 
• Lactating mother
 
 |
| Intervention                          | 
This study compares the standard of care to the standard of care plus the administration of bupivacaine or liposomal bupivacaine in patients receiving craniotomies.
   |
| Statistical Methodology               | 
A Mann-Whitney U test will be used to analyze the primary endpoint of subjects' subjective pain scores. A paired t-test will be used for all secondary endpoints.
  |
| Data and Safety Monitoring Plan       | 
The PI as well as an independent safety monitor ([name]) will be responsible for ensuring subject safety and data integrity.
   |

### Background and Study Rationale

This study will be conducted in full accordance with all applicable University of Pennsylvania Research Policies and Procedures and all applicable Federal and state laws and regulations. All episodes of noncompliance will be documented.

### 1 Introduction

Postoperative pain following craniotomy is a frequent and important cause of distress and hemodynamic instability in the neurosurgical patient population. Current therapeutic options commonly involve the use of systemic intravenous narcotics, which may result in decreased arousal and an inability to complete an adequate neurological examination, an essential component of postoperative care. Targeted cranial blocks with local anesthetic agents have shown to be efficacious in inducing intermediate duration postoperative analgesia. A novel local anesthetic, liposomal bupivacaine, provides up to 72 hours of pain relief in the setting of hemorrhoidectomy, bunionectomy, inguinal hernia repair, total knee arthroplasty and mammoplasty. In this study, we propose to test the investigational agent, liposomal bupivacaine, following craniotomy in a randomized controlled, single-blinded, investigator-initiated study.

### **1.1 Background and Relevant Literature**

Significant postoperative pain following craniotomy affects more than 80% of patients (Mordhorst et al., 2010) and adversely affects patient satisfaction (Myles, Williams, Hendrata, Anderson, & Weeks, 2000). Inadequate post-operative pain control can lead to patient distress, increased sympathetic activity, elevated vital signs (e.g. heart rate, respirations, and blood pressure), increased intracranial pressure and intracerebral hemorrhage. The current standard of care is to manage focal cranial pain with systemic opiate medications, such as morphine and hydromorphone. While systemic administration of opiate medications may achieve a tolerable level of analgesia, they are associated with a degree of risk. Systemic opiates induce respiratory depression, nausea, vomiting, pruritis, hypotension, and sedation, while simultaneously masking the neurological examination (Lai, Ortiz-Cardona, & Bendo, 2012). These opioid-related side effects often lead to a significant increase in total hospital cost, length of stay and acuity of medical care (Oderda et al., 2007). This is contrary to the generally accepted practice of minimizing ICU length of stay for patient safety and cost containment purposes (Beauregard & Friedman, 2003). Postoperative pain is a critical barrier to patient safety and cost effectiveness following routine cranial procedures.

Regional scalp anesthesia for local pain control offers the potential to minimize side effects of systemic opiates while affording patient comfort. Regional scalp analgesia is a safe and effective way of preventing pain during cranial surgery. Using a 1:1 mixture of lidocaine (1% with 1:200,000 epinephrine) and bupivacaine (0.5%), the PI of this proposal routinely performs hemicranial regional blocks for craniotomies at the Hospital of the University of Pennsylvania. Patients are sufficiently comfortable following regional hemicranial block to maintain normal vital signs with low pain scores and participate in complex neuropsychological testing during the operation.

Most currently available local anesthetics have effective analgesic durations of less than 12 hours (Fanelli et al., 1998; Klein et al., 1998). Ropivacaine provides up to 8 hours of analgesia following craniotomy (Nguyen et al., 2001). Bupivacaine scalp blocks result in significant pain reduction for up to four hours and concurrently reduce the need for rescue analgesics (Bala, Gupta, Bhardwaj, Ghai, & Khosla, 2006).

A new ultra-long acting anesthetic appears to produce sustained pain relief for up to three days following a single dose administration. Bupivacaine has recently been formulated with microvesicular liposomes to produce extended-release that persists for up to 10 times longer than bupivacaine HCL. One such example is EXPAREL® (Pacira Pharmaceuticals, Inc, San Diego, CA, USA) containing bupivacaine at a concentration of 13.3 mg/mL. This formulation has been found to be more effective than standard bupivacaine for pain relief in the setting of hemorrhoidectomy (Haas, Onel, Miller, Ragupathi, & White, 2012), bunionectomy, inguinal hernia repair, total knee arthroplasty (Bramlett, Onel, Viscusi, & Jones, 2012), mammoplasty (Smoot, Bergese, Onel, Williams, & Hedden, 2012), and colorectal surgery (Stokes et al., 2019). In these investigations, liposomal bupivacaine was associated with a significant reduction in cumulative pain scores and a significant increase in the median duration until first opiate usage. Furthermore, opioid usage was decreased following liposomal bupivacaine.

The side effect profile of liposomal bupivacaine is similar to bupivacaine HCL and occurs with similar frequency (8-20%) (Baxter, Bramlett, Onel, & Daniels, 2013). Described local toxicities have included granulomatous inflammation, myocyte toxicity, chondrotoxicity and intervertebral disc cell cytotoxicity (Brown & Morrison, 2004; Richard et al., 2011). Some of these toxicities are associated with local anesthetic infusion pumps (Brown and Morrison, Anesthesiology 2004), while others are associated with direct intra-articular or intra-discal injections (Chu, Izzo, Coyle, Papas, & Logar, 2008). Systemic toxicity of liposomal bupivacaine is similar to bupivacaine HCL. Known systemic toxicities of bupivacaine include prolongation of QTc intervals and seizures with high dose, intravenous injection (Naseem et al., 2012). Adverse events associated with liposomal bupivacaine usage were nausea, emesis and hypotension, while showing reductions in constipation, urinary retention and pruritus relative to standard opioid treatment (Brown et al., 2019).

The long-lasting nature of liposomal bupivacaine makes it an attractive candidate for long-lasting postoperative pain relief following supratentorial craniotomy. This study focuses on comparing this novel agent with traditional local anesthetic in producing durable and effective analgesia in cranial blocks after craniotomy.

## **2 Study Objectives**

### **2.1 Primary Objective**

To assess the effectiveness of analgesia by scalp nerve block with various agents in the first 72 hours following elective craniotomy.

## **3 Investigational Plan**

### **3.1 General Design**

We will employ a randomized, single-blinded, prospective study design. Patients will be randomized into one of three treatment groups: Bupivacaine, Liposomal Bupivacaine, and Saline.

### **3.2 Allocation to Interventional Group**

The Neurosurgery Clinical Research Division (NCRD) will generate a randomization table by computer, which assigns subjects 1:1:1 to the three groups, in random blocks of 3 and 6. On the morning of the procedure, subjects will be assigned sequentially to the lowest unassigned randomization number. The surgeon performing the procedure and operating room staff will not be blinded to the intervention, since they will see whether the patient is receiving liposomal bupivacaine, bupivacaine or saline. However, all providers obtaining post-operative data from the patients will be blinded as to which treatment the patient received, in addition to the patient themselves.

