#### **4.5 Subject Recruitment**

We plan to recruit adult patients who are undergoing or preparing to undergo an elective craniotomy for any reason at the Hospital of the University of Pennsylvania (HUP). A craniotomy is a procedure that allows neurosurgeons to access the brain for purposes such as resection of a tumor or clipping of an aneurysm. Patient recruitment will encompass all neurosurgeons practicing at HUP. Informed consent will be obtained from all participants. All consent forms will be retained in a locked file in the NCRD office.

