### Preparation

The anesthesia for each treatment arm will be supplied by the OR pharmacy or the OR Omnicell, as per standard protocol. If the patient is randomized to liposomal bupivacaine (1.33% injection), the OR pharmacy will dispense the medication to the NCRD for transport to the OR for preparation on the field. 20 mL of liposomal bupivacaine will be diluted in 40 mL of sterile, injectable saline (0.9% sodium chloride USP), for a total volume of 60 mL. The surgeon will then draw up the medication for use in a sterile syringe. The patients randomized to bupivacaine (0.25% injection) and placebo (0.9% sodium chloride injection USP) will have the OR nurse obtain the randomized medication from the OR Omnicell per standard practice. 60 mL of the randomized medication will be placed on the sterile field and drawn up into a sterile syringe by the surgeon for use.

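### The protocol prints block sizes of 3 and 6 for one list that unblinded staff can follow and describes no concealment; larger, undisclosed blocks and separate custody of the list would be a nearly free safeguard

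*Combined protocol and SAP*

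**What the plan says.** Section 3.2 describes a computer-generated table that allocates patients 1:1:1 to the three arms "in random blocks of 3 and 6". On the day of surgery, "subjects will be assigned sequentially to the lowest unassigned randomization number". Sections 5 and 5.2.1 repeat both statements under Randomization. No stratification factor is named, and Section 4.2 gives one site and about 90 patients.

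On blinding, Section 3.2 states: "The surgeon performing the procedure and operating room staff will not be blinded to the intervention". Patients are blinded, and "all providers obtaining post-operative data from the patients will be blinded as to which treatment the patient received". Section 4.5 adds: "Patient recruitment will encompass all neurosurgeons practicing at HUP". Section 5.1 places screening at surgical consent, before assignment.

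The documents do not say who holds the table, who performs the assignment, how the next entry is hidden, or who is kept from the block sizes.

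**The concern.** Permuted blocks make later entries in a block depend on earlier ones. The dependence is strongest when blocks are short, when their sizes are known, and when past allocations are visible. All three conditions can occur here: the blocks are short, the protocol states their sizes, and theatre staff see what is injected.

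A person who can foresee the next arm could let it influence whether a patient is put forward or when the case is scheduled. Some eligibility items leave room for judgement, such as the expected neurological state after surgery (Section 5.1) and whether the incision stays within the field of the block (Section 4.4). Because the operator cannot be blinded, concealment before assignment is the main protection against selection bias. One unstratified list of about 90 at a single site has no evident need for blocks of 3.

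**Working it through.** The plan states no predictability figure, so there is none to reproduce.

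**Inputs.** From the documents: three arms, 1:1:1, block sizes 3 and 6 (Section 3.2), N = 90 (Section 4.2). Assumed: the two sizes are equally likely, because the mix is not stated; weights of 1/3 to 2/3 on size 3 are shown as a range.

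**Method.** The observer knows the set of block sizes and all earlier allocations, but not where blocks begin and end. Before each assignment, Bayes' rule gives the probability of each arm. Results average over 3,000 simulated lists of 90.

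**Hand check, third patient on the list.** Suppose the first two patients received different arms, A and B.
- Probability of this is 1 under a block of 3 and 4/5 under a block of 6.
- Posterior probability of a block of 3 = 1/(1 + 0.8) = 5/9.
- Arm C is then certain under a block of 3. Under a block of 6 it has probability 2/4, since one A, one B and two C remain.
- P(C) = 5/9 × 1 + 4/9 × 1/2 = 7/9 = 78%, which is above 75%.
- With weight 1/3 on size 3, the posterior is 1/(1 + 2 × 0.8) = 0.385 and P(C) = 0.385 + 0.615 × 0.5 = 69%, below 75%. So the result depends on the mix.

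**Full observer, equal weights.**

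| Block sizes | Certain | At least 75% probable | Correct guesses (chance 33.3%) |
|---|---|---|---|
| 3, 6 (plan) | 8.6% | 33.3% | 57.6% |
| 6, 9 | 5.1% | 17.8% | 54.0% |
| 6, 9, 12 | 2.4% | 12.3% | 52.5% |
| 9, 12, 15 | 1.9% | 8.1% | 50.6% |

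Simulation error moves these by about 0.1 point. Under the plan, 33.3% of 90 is 30 assignments and 8.6% is about 8. Guesses made at 75% or more are right about 86% of the time. As the weight on size 3 goes from 1/3 to 2/3, the certain share runs from 10.6% to 6.5%, and the share at 75% or more from 25.7% to 33.3%.

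**Block boundaries known (upper bound).** A block of 3 has 1 certain assignment. A block of 6 has 1 + 1/5 = 1.2, because the last two entries match with probability 1/5. Equal mix: (1 + 1.2)/(3 + 6) = 24.4%. For 6, 9 and 12 the figure is 14.1%.

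**Partial observer (400 lists each).** Share predictable with at least 75% probability, by the share of allocations seen at random:

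| Allocations seen | 3, 6 | 6, 9, 12 |
|---|---|---|
| 75% | 11.3% | 1.1% |
| 50% | 2.9% | 0.1% |
| 25% | 0.5% | 0.0% |

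**Gain from 6, 9 and 12 (full observer).**
- Certain: (8.6 − 2.4)/8.6 = 72% fewer.
- At least 75%: (33.3 − 12.3)/33.3 = 63% fewer.
- Excess over chance: 57.6 − 33.3 = 24.3 points falls to 52.5 − 33.3 = 19.2 points, a cut of 5.1/24.3 = 21%.

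**Price of 6, 9 and 12.**
- The largest simulated final gap between arms rises from 2 to 4, and the mean gap from 0.4 to 1.0. At an illustrative standardized difference of 0.76, a 28/32 split has power 83.6% against 83.7% for 30/30 (0.8357 against 0.8373, about 0.2 points).
- The first safety review is at five subjects (Sections 5.6, 7.4.2 and 9.1). If enrolled means randomized, blocks of 3 and 6 always put every arm among the first five. With a first block of 9, an arm is empty with probability 3 × C(6,5)/C(9,5) = 18/126 = 14.3%. With 12 it is 3 × C(8,5)/C(12,5) = 168/792 = 21.2%, and with 6 it is 0. Average: (0 + 14.3 + 21.2)/3 = 11.8%.

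**The case against.** The strongest reply is that few people are full observers. All the hospital's neurosurgeons share the list, and one who sees half the cases can foresee about 3% of assignments. This stands, and it rules out reading the one-third figure as the share that any surgeon would know. The figure needs both complete sight of past allocations and a 75% threshold. A shared theatre team, a coordinator, or surgeons who compare notes come closer to that position; the documents do not say whether anyone reaches it.

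A reader might infer that the research division (NCRD) is the full observer, since it generates the table, carries one product ("the OR pharmacy will dispense the medication to the NCRD for transport to the OR") and stores consents ("All consent forms will be retained in a locked file in the NCRD office"). The documents do not support resting the block-size argument on this. Transport covers the liposomal arm only, stored consent forms reveal no allocation, and Section 3.2 does not say who assigns. Moreover, anyone who holds the table knows every arm whatever the block size. That is a question of custody, and larger blocks do not answer it.

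Timing also limits the harm. Assignment comes on the morning of surgery, after consent, and the calculation looks only one patient ahead. Selective approach at consent would require forecasting past any patients randomized in between, which was not computed. Exclusions for long operations or for the verbal score after extubation come after assignment, when the surgeon can already know the arm, so block size does not affect them. What remains is pre-assignment judgement on eligibility and scheduling, with no described safeguard.

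**Conclusion.** The point holds as a cheap improvement. Printed block sizes, a single sequential list, visible allocations and no described concealment together leave more foreknowledge possible than the trial needs. For a full observer, about 9% of assignments are certain and about 33% are predictable at 75% or more (about 26% to 33% over the assumed mixes). For someone who sees half the cases the latter figure is about 3%.

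Two stronger readings fail. Larger blocks do not remove most predictability in every sense: they cut the confident predictions by roughly two thirds, but the excess of correct guesses over chance by only about a fifth. Nor are they entirely free. Nothing in the documents shows that foreknowledge would be used, so the size of any bias cannot be stated.

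**What to change.** - Delete the block sizes from Sections 3.2, 5 and 5.2.1, and state only that permuted blocks of randomly varying, undisclosed size are used.
- Generate the list, or its unused remainder, with larger randomly mixed blocks such as 6, 9 and 12.
- Add a sentence to Section 3.2 placing the list and block sizes with a named role that does not screen, consent or schedule patients, with each assignment released only on the morning of surgery. This covers the custody gap that block size cannot.

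The work is one regenerated list, edits to three places and one added sentence. The price is a possible final gap between arms of up to 4 patients and about a 12% chance that one arm is empty at the first safety review; the safety officer should be told of the latter.

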### **3.3 Study Measures**

A 10-cm VAS (where '0' is defined as 'no pain at all' and '10' as 'the worst possible pain' will be used to assess subjects' pain score. This will be assessed every 2 hours after extubation postoperatively while the patient is in the ICU, and every 4 hours after the patient has left the ICU, for 72 hours while inpatient, during waking hours, or until discharge in patients discharged prior to 72 hours post-op.

The Glasgow Coma score (GCS) (Teasdale & Jennett, 1974) will also be assessed at the above time points. Patients with GCS verbal score of <4 will be excluded from statistical analysis because of inability to respond to questions after extubation.

The cumulative doses of narcotics during this time period will also be measured. Intravenous narcotic medications will be given by the nurse taking care of the patient as rescue analgesic, as requested by the patient. If the patient requires more analgesics, the dosage will be increased as needed by the patient following standard clinical guidelines. Nursing personnel will be instructed to administer analgesic according to patient demand. The total rescue analgesic requirement will be noted at the above mentioned time intervals.

The duration of time between the end of the surgical procedure (extubation) and the first administration of rescue narcotic will be recorded.

The total length of ICU stay will be recorded. The total length of hospital stay will also be recorded.

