#### **3.4.2 Secondary Study Endpoints**

The secondary outcome variables are the subjects' cumulative narcotic requirement, Glasgow Coma Score, the duration of stay in the intensive care unit (ICU), the duration of time in the hospital until discharge, and the duration of time from the end of surgery to the first administration of narcotic analgesic.

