#### **4.4 Exclusion Criteria**

- Preoperative GCS  $\leq 13$
- Child ( $< 18$  years of age)
- Inability to understand or use the visual analog scale (VAS)
- Proven or suspected allergy to local anesthetics
- Craniotomy incision extending beyond the field of the block
- Patients chronically (more than 2 wk) treated with narcotic medications
- Previous scalp incision
- Bilateral craniotomies
- Allergies to local anesthetics
- GCS verbal score  $< 4$  after extubation
- Patients whose surgeries extend past 6 hours (will be placed on standard of care and removed from study)
- Patients currently on ergot-type oxytotic drugs, MAOIs, or certain antidepressants
- Lactating Mothers

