## 5.1 Screening

Patients will be screened at the time of surgical consenting. Criteria for inclusion will be that the patient:

- Will be undergoing craniotomy.
- Will receive anesthesia.
- Has anticipated normal neurological function post-operatively.
- Does not have allergies to local anesthetics.
- Is not receiving narcotics pre-operatively.

Other inclusion and exclusion criteria as defined above will also apply

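### A verbal GCS score below 4 after extubation, known only after randomisation and the study block, removes the whole patient from analysis, though the stated reason justifies only missing VAS readings

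*Combined protocol and SAP*

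**What the plan says.** Section 3.3 Study Measures has the rule: "Patients with GCS verbal score of <4 will be excluded from statistical analysis because of inability to respond to questions after extubation". The same sentence stands in section 5 and again in 5.2.1, both under Postoperative Data Collection. It names patients rather than readings, and no endpoint. It directly follows the statement that GCS "will also be assessed at the above time points", meaning 2-hourly in the ICU and 4-hourly afterwards.

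The Study Summary lists "GCS verbal score < 4 after extubation" among the exclusion criteria, and 4.4 does the same.

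On timing, 5.1 says "Patients will be screened at the time of surgical consenting". Section 3.2 places allocation on the morning of surgery. Cranial block administration (sections 5 and 5.2.1) has the surgeon give the allocated solution before anaesthesia is lightened and the tube removed.

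Section 3.4.2 makes GCS a secondary endpoint, with cumulative narcotic requirement, time to first narcotic, ICU stay and hospital stay. Section 6 defines no analysis population and no summary measure for GCS.

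**The concern.** An eligibility criterion must be checkable before randomisation, and this one is not. What is left is a removal that depends on the patient's state after treatment. Three things follow.

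- The reason given is narrower than the rule. A patient who cannot answer has no usable VAS reading at that moment, but the other outcomes can still be recorded.
- The verbal score is a component of GCS, which the plan compares between arms. Sections 1 and 1.1 link systemic narcotics to reduced arousal and a masked neurological examination, so an arm difference in the trigger is plausible on the protocol's own account.
- The trigger time is not fixed. The eligibility lists suggest one check at extubation. The position of the rule in 3.3, after repeated GCS, also allows any later score.

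If removals differ by arm, the analysed groups are no longer the randomised groups and the secondary comparisons can be biased. Two analysts following the text could also analyse different sets of patients.

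**Working it through.** **1. Order of events.** Consent and screening, then allocation on the morning of surgery, then craniotomy, study block, extubation and verbal score. The condition comes last, so it cannot act as an eligibility check.

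**2. Does the reason fit each endpoint?**

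| Endpoint | Does inability to answer prevent recording? |
|---|---|
| VAS | Yes, at that reading |
| GCS | No; a low verbal response is itself a score |
| ICU stay, hospital stay | No |
| Narcotic dose, time to first narcotic | No, but "Nursing personnel will be instructed to administer analgesic according to patient demand", so a patient who cannot ask may receive less or later |

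**3. How many patients?** The plan gives no figure. Its 10% dropout allowance (6.1) is for surgical revision or other factors, not for this rule. All rates below are assumptions.

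- One check at q = 1%: 90 × 0.01 = 0.9, about 1 patient.
- Any reading below 4, over k waking readings. Assume 16 waking hours a day for 72 h, so 48 h: k = 12 if 4-hourly, 24 if 2-hourly. The latter needs the full 72 h in the ICU.
  - Independent readings: 1 − 0.99^12 = 0.114 (10.2 of 90); 1 − 0.99^24 = 0.214 (19.3 of 90).
  - Within-patient correlation 0.2 (beta-binomial, a = 0.04, b = 3.96): P(any) = 1 − ∏(b+i)/(a+b+i), i = 0 to k−1, = 0.058 or 0.079 (5.2 or 7.1 of 90).
  - Obtainable VAS readings lost per removed patient, k − kq/P(any): 9.9 and 21.0 at correlation 0.2; 10.9 and 22.9 if independent. A reading-level rule would lose only 1% of readings.

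**4. GCS, one check.** Assume saline has 79% at 15, 20% at 14 and 1% at 13 (removed), and that the block halves the odds of a lower score.

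- Block: P(13) = 0.0050 and P(14 or less) = 0.1173.
- All patients: saline 15 − 0.21 − 0.01 = 14.780; block 15 − 0.1173 − 0.0050 = 14.878; difference 0.098.
- After removal: saline 15 − 0.20/0.99 = 14.798; block 15 − 0.1123/0.9950 = 14.887; difference 0.089.
- Shift 0.009 points. Standard error √((0.192 + 0.117)/30) = 0.10, so just under 0.1 standard errors.

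For an any-reading trigger with a per-patient mean GCS, take 3–10% removed on saline, the same halved odds, and one reading at 13. If the removed patient's other readings are all 14, the difference is understated by up to 0.036 points (28%). If they are all 15, it is overstated by up to 0.011 points (14%). Standard errors are 0.09 to 0.11.

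**5. Narcotic dose.** Assume analysed means of 1 v 0.7, and that removed patients use m times their arm's mean. With pc and pt removed on control and block, the all-patient difference is 0.3 + (m − 1)(pc − 0.7pt).

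| Removed, control v block | m = 1.5 | m = 0.5 | Shift |
|---|---|---|---|
| 1% v 0.5% | 0.303 | 0.297 | 0.003 |
| 5% v 2.5% | 0.316 | 0.284 | 0.016 |
| 10% v 5% | 0.3325 | 0.2675 | 0.033 |
| 10% v 10% | 0.315 | 0.285 | 0.015 |

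With the SD assumed to be half the mean, the standard error is √((0.5² + 0.35²)/30) = 0.111. The unequal rows are 0.03 to 0.3 standard errors. At the extreme any-reading corner (21% v 10.5%) the shift is 0.5 × (0.21 − 0.0735) = 0.068, about 0.6 standard errors. The analysis understates the difference if m = 1.5 and overstates it if m = 0.5.

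**The case against.** The strongest reply is that the rule hardly bites. The words about extubation in the eligibility lists read most naturally as a single check. Patients must have a preoperative GCS above 13, and 5.1 requires that each "Has anticipated normal neurological function post-operatively". At extubation, postoperative narcotic has had little time to act. About one patient is then lost and nothing moves visibly. This stands, and it limits the severity. The larger counts need the less natural trigger and an assumed per-reading rate.

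Second, nurses and patients are blinded (3.2, 5). That limits arm-dependent scoring of the trigger. It does not prevent selection if arousal truly differs by arm.

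Third, a reader might infer that the stated reason is irrelevant to everything except VAS. The documents do not support that. Rescue is on request, so inability to communicate bears on what narcotic dose and time to first narcotic mean. The mismatch is clean only for GCS and the two stay endpoints. For the narcotic endpoints, interpretation may suffer, but recording is still possible.

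Fourth, one could say that exclusion from analysis was meant for VAS only. Nothing in the text narrows it, and the eligibility listing points to the whole patient.

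**Conclusion.** The rule as written is a post-treatment removal of whole patients, selects on a component of a secondary endpoint, and leaves its trigger time open. That follows from the text and needs no assumption. Its numerical effect rests wholly on assumed rates. With one check at 1% it is negligible, about 0.03 to 0.1 standard errors. Under an any-reading trigger at 1% per reading, 5 to 19 of 90 patients could be removed, with modest shifts in secondary comparisons.

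Two stronger readings are tempting but unsupported. One is that the primary VAS comparison is biased: no such bias is shown, and what can be shown is the discarding of obtainable readings under the wider trigger. The other is that the bias favours a particular arm: the direction depends on the trigger, on the GCS summary, and on whether removed patients used more or less narcotic.

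Severity is minor to should-fix. The likely effect is small, but the defect is plain and the repair nearly free.

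**What to change.** 1. Remove no patient from analysis because of the verbal score. Analyse GCS, narcotic use, time to first narcotic, ICU stay and hospital stay in the groups as randomised.
2. For VAS, treat only readings taken while the verbal score is below 4 as missing and keep the patient's other readings. This also settles the one-check or any-reading question. Pre-specify one simple sensitivity analysis, for example varying the imputed value across 0 to 10 and reporting where the conclusion changes.
3. Amend the sentence in 3.3, 5 and 5.2.1, and delete the post-extubation condition from the Study Summary and 4.4. Add an analysis-set statement to 6.2 and reconcile it with the removal of patients whose surgery runs beyond six hours. That removal is in the same lists and is also known only after allocation; unless it is addressed, the contradiction remains.
4. Report affected patients and VAS readings by arm.

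The cost is a short amendment. No new data are needed, and the change concerns analysis rather than treatment. The downside is a little more analysis work and some informatively missing VAS readings to handle openly.
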